## 10.2. Potential Benefits

There may be no direct benefit to the subject from participating in this study. The benefits of receiving a lead implant for His bundle pacing are the same if the patient participates in the study or not.

The Cardiac CT Scan performed in this study is not for diagnostic purposes. However, any potential abnormalities that are identified by the site investigator will be relayed to the subject with instruction for medical follow up.

## 10.3. Risk-Benefit Rationale

All identified risks as described in the previous sections have been successfully mitigated. Any potential risks associated with this study are further minimized by selecting qualified investigators and training study personnel on the CIP. While there may be no benefit of participation in the study there is the potential to aid in collecting information that may lead to new His bundle implant techniques for pacing.

Overall residual risk of participating in the IMAGE-HBP study is considered acceptable.

---

**Medtronic Confidential**

This document is electronically controlled

056-F275, v3.0 Clinical Investigation Plan Template

## 11. Adverse Events and Device Deficiencies

Timely, accurate, and complete reporting and analysis of safety information for clinical studies are crucial for the protection of subjects. Medtronic has established procedures to ensure appropriate reporting of safety information.

### 11.1. Adverse Events

Adverse Event (AE) definitions are provided in **Table 4**. The following AEs will be collected throughout the study duration:

- All AEs related to the Medtronic SelectSecure™ MRI SureScan™ model 3830 lead for His bundle pacing
- Procedure related AEs related to the Medtronic SelectSecure™ MRI SureScan™ model 3830 lead for His bundle pacing
- SAEs resulting in subject death

Events should be reported for the procedure or the lead for His bundle pacing that are considered to be possibly related, probably related or have a causal relationship.

Reporting of these events to Medtronic will occur on an AE eCRF, including date of AE, treatment, resolution, assessment of both the seriousness of the AE and the relatedness to the product. Each AE must be recorded on a separate AE eCRF. Documented pre-existing conditions are not considered AEs unless the nature or severity of the condition has worsened.

For AEs that require immediate reporting (see **Table 6**), initial reporting may be done by phone, email or on the eCRF completing as much information as possible. The original completed AE eCRF must be submitted to Medtronic as soon as possible.

Any medication, whether cardiovascular or not, associated with the treatment of an AE must be reported. Medication changes that are not related to adverse events will not be collected.

Subject deaths are also required to be reported. Refer to Section 11.6 for Subject Death collection and reporting requirements.

### 11.2. Device Deficiencies

Device Deficiency (DD) information will be collected throughout the study and reported to Medtronic. Note that DDs that result in an Adverse Device Effect (ADE) to the subject should be captured on the AE eCRF only. Device Deficiencies that did not lead to an AE but could have led to a Serious Adverse Device Effect (SADE) (i.e. if suitable action had not been taken, if intervention had not been made, or if the circumstances had been less fortunate) require immediate reporting (see **Table 6**). For DDs that require immediate reporting, initial reporting may be done by contacting the study sponsor per the sponsor contact information.

### 11.3. Processing Updates and Resolution

For any changes in status of a previously reported AE (i.e. change in actions taken, change in outcome, change in relatedness), information needs to be updated on, or added to the original AE eCRF. All AEs must be followed until the AE has been resolved, the subject dies or exits the study, or until study closure, whichever occurs first.

At the time of the study exit, all collected AEs with an outcome of “not recovered/not resolved”, “recovering/resolving” or “unknown” must be reviewed and updates provided as applicable.

### 11.4. Definitions/Classifications

Where the definition indicates “device”, it refers to the SelectSecure™ MRI SureScan™ Model 3830 pacing lead for His bundle pacing used in the study.

**Table 4: Adverse Event and Device Deficiency Definitions**

General	
Adverse Event (AE) (ISO 14155:2011, 3.2)	Any untoward medical occurrence, unintended disease or injury, or untoward clinical signs (including abnormal laboratory findings) in subjects, users or other person, whether or not related to the investigational medical device  NOTE 1: This definition includes events related to the investigational medical device or the comparator.  NOTE 2: This definition includes events related to the procedures involved.  NOTE 3: For users or other persons, this definition is restricted to events related to investigational medical devices.
Adverse Device Effect (ADE) (ISO 14155:2011, 3.1)	Adverse event related to the use of an investigational medical device  NOTE 1: This definition includes adverse events resulting from insufficient or inadequate instructions for use, deployment, implantation, installation, or operation, or any malfunction of the investigational medical device.  NOTE 2: This definition includes any event resulting from an error use or from intentional misuse of the investigational medical device.
Device Deficiency (DD) (ISO 14155:2011, 3.15)	Inadequacy of a medical device with respect to its identity, quality, durability, reliability, safety or performance.  NOTE: Device deficiencies include malfunctions, use errors and inadequate labeling.
Relatedness	

# Imaging Study of Lead Implant for His Bundle Pacing Clinical Investigation Plan

056-F275

Version 4.0

Page 38 of 57

Medtronic

Lead for His bundle pacing Related	An adverse event that results from the presence or performance (intended or otherwise) of the lead for HBP
Procedure Related	
An Adverse Event that is directly related to the implantation or surgical modification of the lead for His bundle pacing.
 
NOTE: In general, this excludes events that are inherent to any surgical procedure (e.g. anesthesia complications) as well as indirect subsequent consequences of the procedure (e.g. reaction to pain medication).

Not Related	
Relationship to the device or procedures can be excluded when:
 

• The event is not a known side effect of the product category the device belongs to or of similar devices and procedures;

• The event has no temporal relationship with the use of the investigational device or the procedures;

• The serious event does not follow a known response pattern to the medical device (if the response pattern is previously known) and is biologically implausible;

• The discontinuation of medical device application or the reduction of the level of activation/exposure – when clinically feasible – and reintroduction of its use (or increase of the level of activation/exposure), do not impact on the serious event;

• The event involves a body-site or an organ not expected to be affected by the device or procedure;

• The serious event can be attributed to another cause (e.g. an underlying or concurrent illness/clinical condition, an effect of another device, drug, treatment or other risk factors);

• The event does not depend on a false result given by the investigational device used for diagnosis, when applicable;

• Harms to the subject are not clearly due to use error;

• In order to establish the non-relatedness, not all the criteria listed above might be met at the same time, depending on the type of device/procedures and the serious event.

 
*The study will not be collecting AEs that are not related to the lead for His bundle pacing

---

**Medtronic Confidential**

This document is electronically controlled

056-F275, v3.0 Clinical Investigation Plan Template

# Imaging Study of Lead Implant for His Bundle Pacing Clinical Investigation Plan

056-F275

Version 4.0

Page 39 of 57

Medtronic

Unlikely	
The relationship with the use of the device seems not relevant and/or the event can be reasonably explained by another cause, but additional information may be obtained.
 
*The study will not be collecting AEs that are unlikely related to the lead for His bundle pacing

Possible	
The relationship with the use of the investigational device is weak but cannot be ruled out completely. Alternative causes are also possible (e.g. an underlying or concurrent illness/ clinical condition or/and an effect of another device, drug or treatment). Cases were relatedness cannot be assessed or no information has been obtained should also be classified as possible.

Probably	
The relationship with the use of the investigational device seems relevant and/or the event cannot reasonably be explained by another cause, but additional information may be obtained

Causal Relationship	
The event is associated with the device or study procedures beyond reasonable doubt when:
 

• The event is a known side effect of the product category the device belongs to or of similar devices and procedures;

• The event has a temporal relationship with device use/application or procedures;

• The event involves a body-site or organ that the device or procedures are applied to or the device or procedures have an effect on;

• The serious event follows a known response pattern to the medical device (if the response pattern is previously known);

• The discontinuation of medical device application (or reduction of the level of activation/exposure) and reintroduction of its use (or increase of the level of activation/exposure) impact on the serious event (when clinically feasible);

• Other possible causes (e.g., an underlying or concurrent illness/clinical condition or/and an effect of another device, drug, or treatment) have been adequately ruled out;

• Harm to the subject is due to error in use;

• The event depends on a false result given by the device used for diagnosis (when applicable);

---

**Medtronic Confidential**

This document is electronically controlled

056-F275, v3.0 Clinical Investigation Plan Template

# Imaging Study of Lead Implant for His Bundle Pacing Clinical Investigation Plan

056-F275

Version 4.0

Page 40 of 57

Medtronic

	

• In order to establish the relatedness, not all the criteria listed above might be met at the same time, depending on the type of device/procedures and the serious event.

Seriousness	
Serious Adverse Event (SAE) (ISO 14155:2011, 3.37)	
Adverse event that
 

a) led to death,

b) led to serious deterioration in the health of the subject, that either resulted in

1) a life-threatening illness or injury, or

2) a permanent impairment of a body structure or a body function, or

3) in-patient or prolonged hospitalization, or

4) medical or surgical intervention to prevent life threatening illness or injury or permanent impairment to a body structure or a body function.

c) led to fetal distress, fetal death or a congenital abnormality or birth defect

 
NOTE 1: Planned hospitalization for a pre-existing condition, or a procedure required by the CIP, without serious deterioration in health, is not considered a serious adverse event
 
* The study will be collecting only SAEs that led to a death

Serious Adverse Device Effect (ISO 14155:2011, 3.36)	Adverse device effect that has resulted in any of the consequences characteristic of a serious adverse event.
Complication	
An Adverse event that includes the following is considered a complication:
 

a) Results in death,

b) Involves any termination of significant device function, or

c) Requires an invasive intervention

 
Non-invasive (FDA, CFR 21; 812.3 (k)): when applied to a diagnostic device or procedure, means one that does not by design or intention: Penetrate or pierce the skin or mucous membranes of the body, the ocular cavity, or the urethra, or enter the ear beyond the external auditory canal, the nose beyond the nares, the mouth beyond the pharynx, the anal canal beyond the rectum, or the vagina beyond the cervical os

Observation	Any adverse event that is not a complication

---

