## 9.12. **Assessment of Safety**

Device Deficiencies and Adverse Events related to the procedure or Medtronic SelectSecure™ MRI SureScan™ Model 3830 pacing lead for His bundle pacing will be collected. In addition, all SAEs that result in death will be collected. Further information on the collection and assessment of Adverse Events is discussed in Section 11.

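### A note in Table 4 limits SAE collection to fatal events, contradicting the protocol's other collection rules and putting non-fatal serious complications in Objective 5 at risk

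*Protocol*

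**What the plan says.** The protocol states its adverse event collection rule in several places.

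- **Section 9.12:** "Device Deficiencies and Adverse Events related to the procedure or Medtronic SelectSecure™ MRI SureScan™ Model 3830 pacing lead for His bundle pacing will be collected". The next sentence adds fatal SAEs as a further class. The synopsis (Safety Assessments) and section 11.5.1 follow the same pattern, and 11.5.1 sets the threshold at a possible relationship or stronger.
- **Section 11.1:** the list opens with "All AEs related to the Medtronic SelectSecure™ MRI SureScan™ model 3830 lead for His bundle pacing" and sets no limit on seriousness. Procedure-related events tied to the lead and fatal SAEs are separate bullets.
- **Table 4 (section 11.4), SAE row:** a note under the definition says "The study will be collecting only SAEs that led to a death".
- **Table 4, Not Related row:** "The study will not be collecting AEs that are not related to the lead for His bundle pacing".
- **Table 4, Unlikely row:** "The study will not be collecting AEs that are unlikely related to the lead for His bundle pacing".

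Objective 5 takes its complications from the adverse event eCRF (protocol 13.2.5.2, SAP 7.9.6). The SAP adds a Kaplan-Meier estimate of major complications, whose components include hospitalization, hospital stay prolonged by at least 48 hours, and system revision.

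**The concern.** The SAE note is a collection rule placed in the table that sites use to classify events, and it makes no exception for events related to the lead or procedure. Read literally, a non-fatal serious event caused by the lead, such as a dislodgement that leads to admission and reoperation, is not collected.

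Objective 5 needs exactly that kind of event. A subject whose complications are all left off the form is carried as event-free, so the 12-month complication-free probability rises and the major-complication rate falls. The Cox model in the same objective uses the same events. In a single-arm study with no comparator, nothing in the results would show that this had happened.

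**Working it through.** The plan states no figure on this point that could be reproduced. The check sets the passages side by side.

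**1. Is the contradiction real?**

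| Place | Related, non-fatal SAE | Fatal SAE |
|---|---|---|
| Synopsis, 9.12, 11.5.1 | Collected | Collected, as an addition |
| 11.1 | Collected (no seriousness limit) | Collected, separate bullet |
| Table 6 | Serious adverse device effects go to the sponsor as soon as possible | Same |
| SAP 7.9.6 | Needed for the hospitalization and revision components | Needed |
| Table 4, SAE note | **Not collected** | Collected |

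Table 4 defines a serious adverse device effect by any SAE consequence, not death alone, so Table 6 presupposes that non-fatal serious events reach the sponsor. In-patient or prolonged hospitalization is one of the outcomes in Table 4's SAE definition, and the SAP counts it as a major-complication component. The note therefore conflicts with every other row.

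**2. Do the two relatedness notes exclude procedure events?** Not clearly. Both name only the lead. But the Not Related row itself begins "Relationship to the device or procedures can be excluded when", and Table 4 keeps a Procedure Related row for events directly "related to the implantation or surgical modification of the lead for His bundle pacing". Table 5 has both investigator and sponsor classify relatedness to the procedure. The notes are incomplete rather than a clear exclusion. Taken literally they also shut out unrelated deaths, which 11.1 and 11.6.1 require.

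**3. Is the second bullet of 11.1 at fault?** No. It ties procedure-related events to the lead, as Table 4's own procedure definition does.

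**4. How large could the effect be?** Let c be the number of subjects who truly have a complication and s the share of them whose complications are all omitted. Ignoring censoring, with the protocol's 62 implant attempts:

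recorded proportion = c × (1 − s) / 62

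Both c and s are assumptions; the documents give neither.

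| c (true proportion) | s = 0 | s = 0.25 | s = 0.5 | s = 0.75 | s = 1 |
|---|---|---|---|---|---|
| 3 (4.8%) | 4.8% | 3.6% | 2.4% | 1.2% | 0% |
| 6 (9.7%) | 9.7% | 7.3% | 4.8% | 2.4% | 0% |
| 9 (14.5%) | 14.5% | 10.9% | 7.3% | 3.6% | 0% |

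For example, 6 × (1 − 0.25) / 62 = 4.5 / 62 = 7.3%. The table shows the direction and that the size is open. It supports no particular cell.

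**The case against.** The strongest reply is that no sensible site would follow one note against the rest of the document. Section 11.4 gives definitions, while 11.1 and 11.5.1 set collection. The adverse event form asks for seriousness, Table 5 has investigator and sponsor both classify it, 11.5.1 gives an emergency contact route for serious device effects, and 13.2.5.2 names lead dislodgement as an example complication. The note may only mean that fatal SAEs are the sole SAEs collected regardless of relatedness.

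That makes literal compliance less likely, but it does not remove the contradiction. The milder meaning is not what the note says, and 11.5.1 has events classified by the definitions provided. The safeguards are limited: there is no Clinical Events Committee (section 12), monitoring is conditional (15.1), and the sponsor's review covers events that were reported.

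The objection does defeat several stronger readings that a reader might infer:

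- *Most Objective 5 complications would be lost.* Complication and SAE are separate definitions. Loss of device function or an invasive intervention need not be an SAE, and no serious share is given.
- *The observed rate would be halved.* That needs one site at the section 8.5 cap of half the attempts, omission of every such event there, and all complications being non-fatal SAEs. The documents support none of these beyond the cap itself.
- *Omitted events could not be recovered.* An invasive revision triggers a System Modification CRF (9.10) that records date and reason and lists adverse events among its required items. It is not the stated Objective 5 source, but it would let the sponsor query a missing form.

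**Conclusion.** The point holds as an internal inconsistency, not as a criticism of a design choice. The Table 4 SAE note cannot be reconciled with the synopsis, 9.12, 11.1, 11.5.1 or Table 6. A site that followed it could omit non-fatal serious complications related to the procedure or lead, and Objective 5 would then be biased in the favourable direction. The size depends on how many sites would read the note literally and on how many complications are non-fatal SAEs; the documents fix neither. The lead-only wording of the Not Related and Unlikely notes is a lesser matter of completeness. The implant success endpoint is untouched. The correction is worth making because it is cheap and protects the main safety objective.

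**What to change.** 1. Replace the SAE note in Table 4 with: *All AEs and SAEs related to the procedure or the lead are collected; SAEs not so related are collected only if they led to death.* This restates the rule already in 9.12, 11.1 and 11.5.1.
2. For consistency, complete the ending of the Not Related and Unlikely notes to read: *related to the lead or the procedure, except SAEs that led to death.* Adding the procedure alone would still literally exclude unrelated deaths.
3. Leave the second bullet of 11.1 as it is.

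The cost is three wording changes and a short site training note, carried through the amendment approvals in section 15.6. No visits, forms or analyses change.

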**Medtronic Confidential**

This document is electronically controlled

056-F275, v3.0 Clinical Investigation Plan Template

## 11.5. Reporting of Adverse Events

### 11.5.1. Adverse Event and Device Deficiency Classification

All reported AEs and DDs will be reviewed by a Medtronic representative. AEs will be classified according to the definitions provided.

In this study, Device Deficiencies and Adverse Events classified as **possibly related, probably related or has causal relationship** with the procedure or Medtronic SelectSecure™ MRI SureScan™ Model 3830 pacing lead for His bundle pacing will be collected. In addition, all SAEs that result in death will be collected.

Upon receipt of AEs at Medtronic, a Medtronic representative will review the AE/DD for completeness and accuracy and when necessary will request clarification and/or additional information from the Investigator. Medtronic will utilize MedDRA, The Medical Dictionary for Regulatory Activities (MedDRA), to assign a MedDRA term for each adverse event based on the information provided by the investigator.

Regulatory reporting of AEs and DDs will be completed according to local regulatory requirements. Refer to **Table 6** for a list of required investigator and Medtronic reporting requirements and timeframes. It is the responsibility of the investigator to abide by any additional AE reporting requirements stipulated by the IRB responsible for oversight of the study.

For emergency contact regarding a SADE, contact an IMAGE-HBP Study representative immediately (refer to the study contact list provided in the site's study documents binder/investigator site file or refer to the Sponsor Contact Information section provided in the CIP).

Adverse Events and Deaths will be classified according to the standard definitions as outlined below:

**Table 5: Adverse Event Classification Responsibilities**

What is classified?	Who classifies?	Classification Parameters
Relatedness	Investigator	Lead for His bundle pacing, procedure
	Sponsor	Lead for His bundle pacing, procedure
Seriousness	Investigator	SAE
	Sponsor	SAE
Complication/Observation	Sponsor	Complication, Observation
Diagnosis	Investigator	Based on presenting signs and symptoms and other supporting data
	Sponsor	MedDRA term assigned based on the data provided by Investigator

# Imaging Study of Lead Implant for His Bundle Pacing Clinical Investigation Plan

056-F275

Version 4.0

Page 42 of 57

Medtronic

## 11.5.2. Adverse Event and Device Deficiency Reporting Requirements

Regulatory reporting of AEs and DDs will be completed according to local regulatory requirements. It is the responsibility of the Investigator to abide by the adverse event reporting requirements stipulated by local law and the site's IRB.

**Table 6: Reporting Requirements**

Adverse Device Effects (ADEs)	
Investigator submit to:	
Medtronic	Submit in a timely manner after the investigator first learns of the effect.
Regulatory authorities	Submit to regulatory authority per local reporting requirement.
Institutional Review Board	Submit to Institutional Review Board per local reporting requirement.
Sponsor submit to	
Regulatory authorities	Submit to regulatory authority per local reporting requirement.
Institutional Review Board	Submit to Institutional Review Board per local reporting requirement.
Serious Adverse Device Effects (SADEs)	
Investigator submit to	
Medtronic	Submit to Medtronic as soon as possible
Regulatory authorities	Submit to regulatory authority per local reporting requirement.
Institutional Review Board	Submit to Institutional Review Board per local reporting requirement.
Sponsor submit to	
Regulatory authorities	Submit to regulatory authority per local reporting requirement
Institutional Review Board	Submit to Institutional Review Board per local reporting requirement.
Investigators	Submit per local reporting requirement.
All other reportable Adverse Events	
Investigator submit to	
Medtronic	Submit in a timely manner after the investigator first learns of the effect.
Regulatory authorities	Submit to regulatory authority per local reporting requirement.
Institutional Review Board	Submit to Institutional Review Board per local reporting requirement.
Device Deficiencies with SADE potential	

